2.2.3 Other efficacy variables and analyses

Other efficacy variables are listed along with primary and secondary endpoints in [Table 2-5](#).

Time to moderate or marked improvements in dyspnea assessed by Likert scale through Day 5

Subject-reported dyspnea by Likert scale will be summarized by frequency table at each scheduled time point through Day 5 as defined in protocol. Time to moderately or markedly improvement comparing with baseline will be analyzed by Wilcoxon rank-sum test, based on discrete scheduled hours.

Since the assessment only occurs on the scheduled visits, the nominal scheduled day will be used directly to determine the time to event.

For those subjects without an event, the censoring date will be the earlier of:

- Day 6
- The last date at which the vital status was known, including last visit or contact

AUC of changes from baseline in patient-reported dyspnea by VAS scale through Day 5

The area under the curve of the change from baseline in dyspnea VAS scale (VAS AUC) will be computed by trapezoidal rule after applying the data handling conventions and computations as described below.

Subjects who die or have a worsening heart failure event (either during the index hospital or rehospitalization due to heart failure) will have their score imputed to be the worst observed score in any subject at any time point in the respective analysis population carried forward from the day of death or WHF regardless of whether their original data are missing.

For post-baseline visual analog scale (VAS) values otherwise missing, a missing score will be imputed using linear interpolation between the last preceding and first following non-missing values. If no following non-missing value is available, the last available preceding value will be carried forward. A missing baseline score will be imputed as the earliest, non-missing score within 24 hours for the subject minus the average change from baseline in the study population to that time point; post-baseline scores for subjects for whom a missing baseline cannot be thus imputed will be included in the analysis as no change from baseline. Except for subjects who die or who experience WHF, subjects who are missing all post-baseline dyspnea VAS scores will be included in the analysis as having no change from baseline at any time point.

Descriptive statistics of the area under the curve for the dyspnea VAS change from baseline scores will be presented at each time interval of interest by treatment group. Treatment groups will be compared by presenting the mean difference and corresponding 95% CI and using ANCOVA model with baseline VAS as a covariate.

For those subjects who have at least one post-baseline assessment, their AUC will be approximated by $\sum_{k=2}^m w_k \tilde{y}_k$, where $\tilde{y}_k = 0.5(y_k + y_{k-1})$, $w_k = (t_k - t_{k-1})/(t_m - t_1)$, and y_j is the change-from-baseline in dyspnea VAS value at time t_j , for $j = 1, \dots, m$, in which $t_1 < \dots < t_m$. m is the number of measurements for a subject and t_1 is time of the baseline, that is, $t_1 = 0$ and $y_1 = 0$. The scheduled time will be used in the calculation.

In addition, descriptive statistics for the baseline values, the post-baseline values, and the change from baseline value will be provided at each scheduled time point by treatment group.

Length of stay in index ICU/CCU

The length (days) of stay in ICU/CCU will be obtained from eCRF page directly. If the information is missing in eCRF page or subjects who die during the initial hospitalization, the maximum number of days in the ICU/CCU over all subjects in FAS will be assigned. It will be analyzed using a Wilcoxon rank sum test.

Renal dysfunction or in-hospital worsening of renal function through Day 5

Worsening renal function is defined as an increase in serum creatinine of ≥ 0.3 mg/L (27 $\mu\text{mol/L}$), from the values measured at baseline. A subject who meets the criteria at any time during the 5 days after infusion will be counted once; the chi-squared test will be performed for comparing two treatments.

Number and percentage of subjects will be displayed by treatment and visit for the following category: ≥ 0.3 mg/L increase in serum creatinine.

Additional summaries of serum creatinine and eGFR are discussed in [Section 2.4.2.2](#), Clinical chemistry.

Time to CV death or rehospitalization due to heart failure (HF)/renal failure (RF) through Day 180

Time-to-event (in days) will be calculated using time of first event of adjudicated CV death or adjudicated rehospitalization due to HF/RF minus time of randomization. If the reason for adjudicated death or rehospitalization is unknown, it will be considered as the event. The analysis and censoring method will be performed similarly to time-to-CV death.

Time to rehospitalization due to heart failure (HF) or renal failure (RF) through Day 180

Time-to-event (in days) will be calculated using time of first event of adjudicated rehospitalization due to HF or RF minus time of randomization. If the reason for adjudicated rehospitalization is unknown, it will be considered as the event.

The analysis and censoring method will be performed similarly to time-to-all-cause-death.

Due to competing risk between death and rehospitalization, the difference in mortality between the treatment groups may mislead the results. In this case, the composite endpoint of Time to CV death or rehospitalization due to heart failure (HF)/renal failure (RF) through Day 180 provides more reliable results.

Time to in-hospital worsening heart failure through Day 5 by symptoms and signs

Time-to-event (in days) will be calculated using time of first event of in-hospital worsening heart failure through Day 5. The worsening heart failure is defined by symptoms only, signs only, and by both symptoms and signs. The analysis and censoring method will be performed similarly to time-to-WHF.

Use of IV loop diuretic and vasoactive agents through Day 5

The subjects with intravenous diuretic and vasoactive therapy (yes/no) during 5 days after study medication infusion will be analyzed using chi-squared test.

The medications of interest are collected in two eCRF pages: “IV loop diuretic medications for heart failure” and “IV medications other than loop diuretics” ([Section 2.1.10](#)). The summaries of doses for those medications are also addressed in [Section 2.1.10](#).

Change from baseline in cardio-renal biomarkers through Day 2 and Day 5

Biomarkers related to cardiac and renal function/injury including but not limited to high sensitivity troponin T, NT-proBNP, and Cystatin C will be collected at baseline, at 48 hours (Day 2) and 120 hours (Day 5) post infusion. This list of potential biomarkers may be changed or expanded further as it is recognized that more relevant or novel biomarkers may be discovered.

Details are described in the separate biomarker statistical analysis plan.

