### **Other efficacy variables**

Other efficacy variables will comprise:

1. Time to moderate or marked improvements in dyspnea by Likert scale through Day 5
2. Dyspnea by VAS-AUC changes through Day 5
3. Length of stay in index ICU/CCU
4. Renal dysfunction & prevention of in-hospital worsening of renal function through Day 5
5. Time to re-hospitalization due to HF and renal failure through Day 180
6. Time to CV death or re-hospitalization due to HF/RF through Day 180
7. Time to in-hospital worsening heart failure through Day 5 where the in-hospital worsening heart failure is defined by symptoms only, signs only, and by both symptoms and signs
8. Use of loop diuretics and vasoactive agents through Day 5
9. Changes in cardio-renal biomarkers (Days 2 and 5)

Time to moderate or marked improvements in dyspnea by Likert scale through Day 5 (variable number 1) will be analyzed by Wilcoxon rank-sum test. Other time to event variables (5, 6 and 7) will be analyzed by presenting Kaplan-Meier estimates and testing with the log rank test. Change from baseline variables (2) will be analyzed using ANCOVA model with baseline VAS as a covariate. Variables representing the number of days or multi-categorical variables (3) will be analyzed using the Wilcoxon rank-sum test. The categorical variables (4 and 8) will be analyzed using chi-squared tests.

Detailed biomarker analyses (9) (changes in cardio-renal biomarkers at Days 2 and 5) will be included in the Statistical Analysis Plan.

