2.2 Efficacy evaluation

The Full Analysis Set (FAS) is the primary analysis population for efficacy analyses, following the intention-to-treat principle. Per-protocol (PPS) population will be used in the supportive analysis for primary and key secondary efficacy parameters (Table 2-5).

Table 2-5 List of efficacy endpoints and analyses

Endpoint	Analysis set	Analysis method
Primary efficacy endpoint ($\alpha=0.025$, 1-sided)		
1 Trichotomous composite (success, failure, no change)	FAS/PPS	Ordered logistic-regression (proportional odds) model that includes treatment and [REDACTED] as factors (primary analysis is on FAS)
	FAS	Ordered logistic-regression model including treatment only (sensitivity analysis 1)
	FAS	van Elteren extension of the Wilcoxon test stratified by [REDACTED] (sensitivity analysis 2)
Secondary efficacy endpoints (if primary endpoint is significant, then test in the order listed below at $\alpha=0.05$ each)		
1 Time (hours) to WHF through Day 5	FAS/PPS	Gehan's generalized Wilcoxon test
2 Time (days) to CV death through Day 180	FAS/PPS	Kaplan-Meier estimates and log-rank test
3 Time (days) to all-cause death through Day 180.	FAS	Kaplan-Meier estimates and log-rank test
Other efficacy endpoints (at $\alpha=0.05$, no multiplicity adjustment)		
1 Time (hours) to moderate or marked improvements in dyspnea by Likert scale through Day 5	FAS	Wilcoxon rank-sum test
2 Dyspnea by VAS-AUC changes (from baseline) through Day 5	FAS	ANCOVA
3 Length of stay (# of days) in index ICU/CCU	FAS	Wilcoxon rank-sum test
4 Renal dysfunction or worsening of renal function through Day 5	FAS	chi-squared test
5 Time (days) to re-hospitalization due to HF and renal failure through Day 180	FAS	Kaplan-Meier estimates and log rank test
6 Time (days) to CV death or re-hospitalization due to HF/RF through Day 180	FAS	Kaplan-Meier estimates and log rank test
7 Time to in-hospital worsening heart failure through Day 5 defined by symptoms and signs		Kaplan-Meier estimates and log rank test
8 Use of loop diuretics and vasoactive agents through Day 5	FAS	chi-squared test
9 Changes in cardio-renal biomarkers (Day 2 and Day 5)	FAS	Summary statistics, see Section 2.2.3

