2.2.2 Secondary efficacy variables and analyses

There are three secondary variables:

- WHF through Day 5
- CV death through Day 180
- All-cause death through Day 180

All of these secondary variables are time-to-event variables. The hypothesis will be tested based on the FAS at a significance level of 0.025 (one-sided).

The three secondary variables will be tested using hierarchical testing procedure in controlling overall α of 0.05 (Bretz et al 2009). If primary endpoint is significant, WHF will be tested first at α of 0.05. If WHF is significant at the same α level then will proceed to test CV death and only if CV death is significant then will test all-cause death at α of 0.05.

WHF through Day 5

Time to WHF through Day 5 will be analyzed using Gehan's generalized Wilcoxon test. Subjects died in the 5-day period will be considered as having WHF event. Event date and time will be used at calculating the time to event for better precision, and convert it back to days.

Time-to-event (days) = (first event date/time – baseline date/time),

For those subjects without events, the censoring date will be the earlier of

- Hour 120 (5 days)
- The last date at which the vital status was known, including last visit or contact

Kaplan-Meier curves will be presented graphically by treatment group and Kaplan-Meier estimates for selected time points with 95% confidence intervals will be tabulated.

In addition, analyses will be performed using a modified definition of WHF, e.g. subjects with (1) worsening signs AND symptoms or (2) IV intervention and/or mechanical support. Another sensitivity analyses that exclude subjects whose only symptom is abdominal bloating/discomfort or fatigue/decreased exercise tolerance will also be provided.

CV death through Day 180

CV death will be analyzed with a log-rank test. The time-to-event will be calculated days by subtracting the randomization date from the event date. Number and percentage of subjects who died from cardiovascular reasons based on the number of subjects in the population as denominator will be provided by treatment group. The hazard ratio (relative risk) and its associated two-sided 95% confidence interval will be estimated based on a Cox proportional hazards model with treatment assignment as a factor.

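### Time to Likert dyspnea improvement: the rank-sum test cannot use the SAP's censoring rule, so an unimproved patient who dies or is lost before Day 6 ranks ahead of surviving non-improvers

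*SAP*

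**What the plan says.** The test is named in three places. SAP 2.2.3: "Time to moderately or markedly improvement comparing with baseline will be analyzed by Wilcoxon rank-sum test, based on discrete scheduled hours". Protocol 9.5.1 (Other efficacy variables): "Time to moderate or marked improvements in dyspnea by Likert scale through Day 5 (variable number 1) will be analyzed by Wilcoxon rank-sum test". SAP Table 2-5 names the same test for the endpoint it calls "Time (hours) to moderate or marked improvements in dyspnea by Likert scale through Day 5".

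SAP 2.2.3 then sets a censoring date for patients without an event. It is the earlier of Day 6 and a second limb: "The last date at which the vital status was known, including last visit or contact". The SAP does not say how a censored time enters the rank-sum test, and it has no separate rule for deaths on this endpoint.

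Three other endpoints are handled differently:

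- VAS-AUC (SAP 2.2.3): patients who die or have worsening heart failure (WHF) "will have their score imputed to be the worst observed score in any subject at any time point in the respective analysis population".
- ICU/CCU stay (SAP 2.2.3), also a rank-sum test: for "subjects who die during the initial hospitalization, the maximum number of days in the ICU/CCU over all subjects in FAS will be assigned".
- WHF (SAP 2.2.2): "Time to WHF through Day 5 will be analyzed using Gehan's generalized Wilcoxon test".

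The time unit is also unsettled. The test sentence speaks of scheduled hours, but the next sentence says "the nominal scheduled day will be used directly to determine the time to event". Table 2-5 says hours.

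**The concern.** A rank-sum test takes one number per patient and orders the numbers. It cannot record that a patient had not improved by the time shown. If the censoring time is the number supplied, the two limbs of the rule behave differently. Day 6 is later than any scheduled Likert assessment, so a non-improver alive at Day 6 correctly receives the slowest value. A patient who dies unimproved, or whose vital status is lost, before Day 6 receives a short time and is counted as a fast improver.

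The error always favours the arm with more early deaths or losses. If serelaxin reduced early deaths, it would work against serelaxin; if serelaxin increased them, it would hide harm. It also leaves the Likert endpoint as the only one of these measures on which an early death can look like a good outcome.

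**Working it through.** **1. Figures in the documents.** The plan gives no power, event or exit figure for this endpoint, so there is none to reproduce. The arm size comes from the 1,520 patients randomized 1:1 (SAP 2.7), or 760 per arm. That total does reproduce. Whitehead's formula is N = 12(z_0.975 + z_0.80)² / [ln(0.75)² × (1 − Σp̄³)]. The RELAX-AHF placebo split in Protocol 6.4.3 (11.9% failure, 26.0% success, hence 62.1% neither) gives N = 1,511.

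**2. Ranks in a six-patient example.**

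| Patient | Time ranked | Rank as written | Rank if death is strictly worst |
|---|---|---|---|
| Improved at 6 h | 6 | 1 | 1 |
| Unimproved, died at 30 h | 30 | 2 | 6 |
| Improved at 48 h | 48 | 3 | 2 |
| Improved at 120 h | 120 | 4 | 3 |
| Two alive, unimproved at Day 6 | 144 | 5.5 each | 4.5 each |

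The death ranks ahead of both surviving non-improvers and of two patients who did improve.

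**3. Size in closed form.** Assumed improvement times, the same in both arms: 6/24/48/72/96/120 h/never = 25/25/17/8/4/3/18%. A patient leaving on Day d is coded 24d hours, and never is coded 144 h.

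Mid-percentiles (cumulative share below, plus half the tied share):

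- 24 h: 25 + 12.5 = 37.5
- 48 h: 50 + 8.5 = 58.5
- 72 h: 67 + 4 = 71
- 96 h: 75 + 2 = 77
- 120 h: 79 + 1.5 = 80.5
- never: 82 + 9 = 91

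The null standard error of the Mann-Whitney probability is √[(1 − Σp³) × 1,520 / (12 × 760²)]. With Σp³ = 0.0426 this is 0.0145.

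Shift in z = (difference in exit rates) × (0.91 − mean percentile of exits) / 0.0145. At 4% versus 2%:

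- Exits on Days 1-2: mean percentile (37.5 + 58.5)/2 = 48.0, so 0.02 × 0.43 / 0.0145 = 0.59.
- Exits on Days 3-5: mean percentile (71 + 77 + 80.5)/3 = 76.2, so 0.02 × 0.148 / 0.0145 = 0.20.

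**4. Simulation under the same assumptions** (2,000 trials per cell, tie-corrected z, Monte Carlo standard error of each mean z about 0.02). The shift compares the rule as written with exits placed at Day 6.

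| Exits, placebo vs serelaxin | Exits on Days 3-5 | Exits on Days 1-2 |
|---|---|---|
| 1% vs 0.5% | 0.05 | 0.16 |
| 2% vs 1% | 0.09 | 0.27 |
| 4% vs 2% | 0.20 | 0.59 |
| 2% vs 2% | 0.00 | 0.00 |

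The shifts agree within 0.02 whether exits come from all patients or only from never-improvers. When they come only from never-improvers, the arms have identical improvement and z should be zero. At 4% versus 2% the mean z as written is +0.38 for exits on Days 1-5, +0.60 for Days 1-2 and +0.22 for Days 3-5 (positive favours placebo). With the worst value it is +0.02, +0.01 and +0.01.

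**5. A second simulation with other assumptions** (25% or 35% non-improvers, improvement more spread out, exits uniform between 6 and 120 h, 1,500 runs). Mean z as written is +0.31 to +0.33 at 2% versus 1%, +0.55 to +0.59 at 3% versus 1%, and about 0 at 1% versus 1%. At 5% versus 2% it is +0.87, and the chance of a false result favouring placebo is about 14% against a nominal 2.5%.

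**6. Time unit.** Protocol Table 6-1 labels the Hour 6 and Hour 24 Likert assessments both as Day 1. Under the day wording, improvers at 6 h and 24 h are tied; under the hours wording they are not.

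**The case against.** The strongest reply is that nothing says a death is censored at its date. For CV death the SAP lists non-CV death as a bullet separate from last known vital status. For WHF and all-cause death, early deaths are events. A patient who died on Day 2 has a known status at Day 6, so the rule could yield Day 6, which is the recommended value. Only true losses would then remain, and the protocol limits these: patients discharged early return for Day 5 (Table 6-1, footnote b), survival status is pursued through informants (Section 6), and loss to follow-up cannot be declared before the end-of-study visit is due (5.5.11).

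This reading fails on the SAP's own usage. Time to re-hospitalization (SAP 2.2.3) borrows the all-cause-death censoring rule, which has no date-of-death bullet. A death is not an event for re-hospitalization, so deaths there must be censored through the vital-status limb. The safeguards reduce losses but not deaths.

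It could also be said that Gehan's test was meant, or that the censoring date serves only Kaplan-Meier curves. Gehan's test is named separately for WHF, while three places name the rank-sum test here. If the date serves only the curves, the test has no rule for non-improvers at all.

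Some of the reply stands. The SAP does not state that the censoring time is the ranked value, although that is the direct reading. The exit rates and improvement times are assumed. Giving deaths the worst value is a choice of estimand: with exits drawn from all patients at 4% versus 2%, mean z moves from between −0.37 and +0.01 to between −0.58 and −0.52, although underlying improvement times are equal. It is, however, the choice the SAP makes for VAS-AUC and ICU/CCU stay. The hours/day conflict is editorial and adds little weight.

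**Conclusion.** The concern holds. As written, the rule gives an unimproved patient who dies or is lost before Day 6 a better rank than a surviving non-improver, and better than some patients who improved later.

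The effect is modest: a z shift of 0.05 to 0.59 over assumed exit rates from 1% versus 0.5% to 4% versus 2%, and none when exits are balanced. The nearest figure in the documents is RELAX-AHF treatment failure through Day 5, 11.9% on placebo and 6.4% on serelaxin (Protocol 6.4.3). It combines WHF, re-hospitalization and death, so it is only a ceiling for deaths. The direction and the ranking error do not depend on the assumed rates.

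This is an other efficacy endpoint, tested at 0.05 without multiplicity adjustment, so no primary or secondary conclusion changes. It should be corrected before unblinding, because two programmers could obtain different p-values from the present text.

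**What to change.** In SAP 2.2.3, give unimproved patients who die before Day 6 the worst value (Day 6 or beyond). Then choose one of:

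- (a) Keep the rank-sum test and give all other non-improvers the same value. This keeps the test in Protocol 9.5.1 and is the simpler change.
- (b) Use Gehan's generalized Wilcoxon test, with losses censored at their last Likert assessment. Deaths still need the worst value, since Gehan's test alone would treat them as uninformative censoring. This departs from the test named in Protocol 9.5.1 and should be recorded as a change.

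The options differ little. In the all-patient scenario at 4% versus 2%, mean z for exits on Days 1-5, 1-2 and 3-5 is −0.52, −0.58 and −0.57 with all exits at the worst value. It is −0.48, −0.50 and −0.56 under Gehan's test with half the exits as deaths and half as censored losses.

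Also state whether in-hospital WHF is handled as in VAS-AUC, and replace the nominal day with the nominal scheduled hour (6, 24, 48, 72, 96, 120) to agree with Table 2-5.

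The cost is a few lines of SAP text and at most a different test call. No new data and no sample-size change are needed.

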In addition, the Kaplan-Meier estimates of the survival functions for each treatment group will be plotted. The Kaplan-Meier estimates of the cumulative event rate will also be presented in tables by treatment group for each day and also by time interval.

For CV death, a patient without an event will be censored at the earlier of:

- Date of death for non-CV related causes
- The last date at which the vital status was known, including last visit or contact
- Day 180

An adjudicated death with unknown cause will be classified as a CV death. Similarly, investigator suspected deaths of unknown cause will be classified as CV deaths.

All-cause death through Day 180

All-cause death through Day 180 will be analyzed similarly to CV death through Day 180. A patient without an event will be censored at the last date at which the vital status was known (including last visit or contact) or at Day 180.

Of note, CV death and all-cause death will be two efficacy variables for bridging with other global studies.

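### The rule borrowed for time to HF/RF re-hospitalization is silent on death before readmission; if such deaths are censored, the Kaplan-Meier rates modestly overstate the probability of readmission

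*SAP*

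**What the plan says.** SAP Table 2-5 lists "Time (days) to re-hospitalization due to HF and renal failure through Day 180" as other efficacy endpoint 5, outside the testing hierarchy, with Kaplan-Meier estimates and a log-rank test. The Protocol agrees, under Other efficacy variables: "Other time to event variables (5, 6 and 7) will be analyzed by presenting Kaplan-Meier estimates and testing with the log rank test".

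SAP 2.2.3 counts the first adjudicated HF or RF re-hospitalization as the event, or one whose reason is unknown. It then borrows its rules: "The analysis and censoring method will be performed similarly to time-to-all-cause-death".

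The borrowed rules are in SAP 2.2.2. Under them, anyone still event-free "will be censored at the last date at which the vital status was known (including last visit or contact) or at Day 180". The analysis there is itself borrowed: "All-cause death through Day 180 will be analyzed similarly to CV death through Day 180". For CV death the plan includes a Cox hazard ratio and absolute rates: "The Kaplan-Meier estimates of the cumulative event rate will also be presented in tables by treatment group".

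SAP 2.2.3 acknowledges the difficulty: "Due to competing risk between death and rehospitalization, the difference in mortality between the treatment groups may mislead the results". It then calls the composite of CV death or HF/RF re-hospitalization (Table 2-5, row 6) more reliable. That composite follows the CV-death censoring rule, under which a non-CV death is censored on its date. The text available plans no cumulative incidence estimate for either endpoint.

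**The concern.** A patient who has died can no longer be readmitted. If death is treated as ordinary censoring, Kaplan-Meier in effect assumes that the dead would have gone on to be readmitted at the same rate as the survivors. One minus the estimate then describes readmission in a setting without death, and is not the proportion of randomized patients who are readmitted by Day 180.

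What is at stake is how the tabulated rates and curves are read. A clinician or a health-economic user will take them as probabilities. Lower mortality on serelaxin is a secondary hypothesis. If it holds, the overstatement is larger on placebo than on serelaxin.

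**Working it through.** **Figures in the plan.** The documents give no readmission rate, event count or power for this endpoint, so there is no planned figure to reproduce. The sample size of 1,520 was set for the primary composite and is used here only for arm size (1,520/2 = 760).

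**How the rule treats a death before readmission.**

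1. The event is readmission only, so the patient has no event.
2. The censoring time is the last date of known vital status or Day 180. For a patient who died, the first is most naturally the date of death.
3. The rule has no line for deaths because under all-cause death they are the events. Censoring at death is therefore an inference.
4. If such patients were instead carried event-free to Day 180, Kaplan-Meier would equal the cumulative incidence apart from other censoring, and the bias would largely vanish.

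**Inputs for the size, assuming censoring at death.**

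- Kaplan-Meier readmission rate at Day 180: 15%, 20% and 25% (assumed).
- Mortality at Day 180, lower value: 8% (assumed).
- Mortality at Day 180, upper value: 15.8%. Protocol 1.1 quotes general AHF mortality of 10.4% at 30 days and 22% at 1 year. With a constant hazard between those times, the daily hazard is ln(0.896/0.780)/335 = 0.000414, and 1 - 0.896 × exp(-0.000414 × 150) = 0.158. This is not an estimate for this trial.
- Constant hazards, the same death hazard before and after readmission, and no other loss to follow-up (assumed).

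**Formulas.** With KM the Kaplan-Meier readmission rate and D the mortality, a = -ln(1 - KM) and b = -ln(1 - D). The actual cumulative incidence is CIF = a/(a + b) × [1 - exp(-(a + b))].

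For example, KM 20% and D 8% give a = 0.2231, b = 0.0834 and CIF = 19.2%.

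| KM | D | CIF | Overstatement (points) | Relative to CIF |
|---|---|---|---|---|
| 15% | 8% | 14.4% | 0.6 | 4.1% |
| 15% | 15.8% | 13.8% | 1.2 | 8.6% |
| 20% | 8% | 19.2% | 0.8 | 4.1% |
| 20% | 15.8% | 18.4% | 1.6 | 8.5% |
| 25% | 8% | 24.0% | 1.0 | 4.0% |
| 25% | 15.8% | 23.1% | 1.9 | 8.4% |

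**Sensitivity to constant hazards.** The general mortality figures are front-loaded: 10.4/15.8, about two-thirds, of the 180-day deaths fall in the first 30 days. With that shape and a constant readmission hazard, the overstatement is 1.8 points at KM 15% and 2.9 points at KM 25%, about 13% relative. So the upper end of the table is not a ceiling.

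**Difference between arms.** Assume the same readmission hazard in both arms (KM 20%, a = 0.2231), placebo mortality of 10% (b = 0.1054) and a mortality hazard ratio of 0.63. The last matches the 37% reduction that Protocol 1.1 reports for the earlier trial (b = 0.1054 × 0.63 = 0.0664).

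- Placebo: CIF 19.02%, overstatement 0.98 points.
- Serelaxin: CIF 19.37%, overstatement 0.63 points.

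Kaplan-Meier shows equal rates where the actual probabilities differ by 0.35 points. For scale, the 95% half-width for a difference between two 20% rates at 760 per arm is 1.96 × √(2 × 0.2 × 0.8/760) = 4.0 points.

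**The case against.** A reader might infer that the plan's readmission rates are certain to be overstated. The documents do not support that. No sentence says that deaths are censored at death for this endpoint, whereas the CV-death rule does say so for non-CV deaths. The firm defect is that the handling is unstated; the overstatement follows only on the more natural reading.

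A reader might also infer that the treatment comparison is invalid. It is not. With deaths censored, the log-rank test compares cause-specific readmission hazards, which is a legitimate question. One minus Kaplan-Meier is also a recognised net-risk quantity, and misleads only when read as an actual probability. The arm-dependent part is under a tenth of the confidence half-width in the illustration above.

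The SAP names the competing risk and directs the reader to the composite. There, CV deaths and deaths of unknown cause count as events, which narrows the gap. That mitigation is partial: the composite does not estimate the readmission rate, and non-CV deaths are still censored in it.

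Finally, the size rests on inputs that the documents do not give for this trial. That objection stands, and the range is illustrative only. What survives is that the plan tabulates absolute rates by an estimator which, on its most natural reading, does not give the probability of readmission.

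**Conclusion.** The point holds as a reporting matter of low severity. Table 2-5 row 5 relies on a censoring rule that does not address death before readmission. If those patients are censored at death, the Kaplan-Meier rates overstate the probability of readmission by about 0.6-1.9 points (about 4-9% relative to the true incidence). This assumes Kaplan-Meier rates of 15-25%, 180-day mortality of 8-16% and constant hazards. Early clustering of deaths could make it larger, and carrying deaths event-free to Day 180 would largely remove it. The distortion between arms is small. The endpoint lies outside the hierarchy, so the sample size and the primary and key secondary conclusions are untouched.

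**What to change.** - **SAP 2.2.3:** state that death before readmission is a competing event for time to HF/RF re-hospitalization, instead of relying on the all-cause-death rule.
- **Table 2-5, row 5:** replace the Kaplan-Meier rates and curves by Aalen-Johansen cumulative incidence by arm, with death as the competing event, and show deaths without readmission alongside.
- **Table 2-5, row 6:** do the same, with non-CV death as the competing event. For consistency, apply this also to the tabulated CV-death rates in SAP 2.2.2, which censor non-CV deaths in the same way.
- **Tests:** keep the log-rank and Cox results and label them as cause-specific.

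The cost is minor reprogramming of tables and figures. Protocol 8.5 already has deaths classified and re-hospitalizations adjudicated by the CEC, so no new data, visits or alpha are needed.
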